7.4. Participant Discontinuation/Withdrawal From the Study

Each participant has the right to withdraw from the study at any time for any reason without affecting the right to treatment by the investigator. The investigator should make an attempt to contact participants who did not return for scheduled visits or follow-up. Although the participant is not obliged to give reason(s) for withdrawing prematurely, the investigator should make a reasonable effort to ascertain the reason(s) while fully respecting the participant's rights.

A participant will be withdrawn from the study for any of the following reasons:

- Lost to follow-up
- Withdrawal of consent
- Death
- Repeated failure to comply with protocol requirements or to cooperate with the study-site personnel
- Decision by the sponsor or the investigator to stop or cancel the study
- Decision by local regulatory authorities or IEC/IRB to stop or cancel the study

Any unnecessary study discontinuation should be avoided. When a participant withdraws before study completion, the reason for withdrawal is to be documented in the eCRF and in the source document. All efforts should be made to complete and report the observations as thoroughly as possible. Study vaccine assigned to the withdrawn participant may not be assigned to another participant. Participants who withdraw will be replaced, as long as the participant has not been vaccinated (Section 6.3).

An early exit visit will be conducted for those participants who are unable to continue participation in the study and withdraw from the study before Day 183, but who do not withdraw consent (Section 1.3). Participants who wish to withdraw consent from participation in the study will be offered an early exit visit (prior to formal withdrawal of consent). They have the right to refuse.

If a participant is lost to follow-up, every reasonable effort must be made by the study-site personnel to contact the participant and determine the reason(s) for discontinuation/withdrawal. The measures taken to follow up must be documented.

7.4.1. Withdrawal From the Use of Research Samples

Withdrawal From the Use of Samples in Future Research

The participant may withdraw consent for use of samples for research (refer to Long-term Retention of Samples for Additional Future Research in Section 10.4, Appendix 4). In such a case, samples will be destroyed after they are no longer needed for the clinical study. Details of the sample retention for research are presented in the main ICF.

7.5. Lost to Follow-up

A participant will be considered lost to follow-up if he or she repeatedly fails to return for scheduled visits and is unable to be contacted by the study site. A participant cannot be deemed lost to follow-up until all reasonable efforts made by the study-site personnel to contact the participant are deemed futile. The following actions must be taken if a participant fails to return to the study site for a required study visit:

- The study-site personnel must attempt to contact the participant to reschedule the missed visit as soon as possible, to counsel the participant on the importance of maintaining the assigned visit schedule, to ascertain whether the participant wishes to or should continue in the study.
- Before a participant is deemed lost to follow-up, the study-site personnel must make every reasonable effort to regain contact with the participant (where possible, 3 telephone calls, e-mails, fax, and, if necessary, a certified letter to the participant's last known mailing address, or local equivalent methods), and to determine the reason for discontinuation/withdrawal. These contact attempts should be documented in the participant's study file.
- Should the participant continue to be unreachable, he or she will be considered to have withdrawn from the study.

Should a study site close, eg, for operational, financial, or other reasons, and the investigator cannot reach the participants to inform them, their contact information will be transferred to another study site.

8. STUDY ASSESSMENTS AND PROCEDURES

Overview

The Schedule of Activities (Section 1.3) summarizes the frequency and timing of immunogenicity and safety measurements applicable to this study. Unscheduled visits may be performed based on the investigator's clinical judgment and may include further evaluations, as needed.

In addition, a participant diary to record body temperature and solicited injection site and systemic signs and symptoms will be provided to the participants on the day of study vaccination (Day 1). The participant diary includes instructions on how to capture the data and grading scales to assess severity of the signs and symptoms. The study-site personnel will be responsible for providing appropriate training to the participant to avoid missing or incorrect data. The participant diary will be reviewed by the study-site personnel at the Day 8 visit. If the participant diary review is missed, the participant diary will be reviewed during the following visit. Thermometers will be given to all participants on the day of study vaccination (Day 1) and should be returned to the study site at the end of the study/early withdrawal. Participants will also be provided with a ruler on the day of study vaccination (Day 1) to measure local injection site reactions.

If multiple assessments are scheduled for the same timepoint, it is recommended that procedures be performed in the following sequence: vital signs, nasal sampling, blood draws. If needed, assessments may be performed on another day within the applicable visit window. Actual dates and times of assessments will be recorded in the source document and in the eCRF.

The total blood volume to be collected from each participant will be approximately 240 mL (Cohort 1) or 260 mL (Cohorts 2 and 3).

Repeat or unscheduled samples may be taken for safety reasons or for technical issues with the samples.

Sample Collection and Handling

The actual dates and times of sample collection must be recorded in the eCRF or laboratory requisition form.

Refer to the Schedule of Activities (Section 1.3) for the timing and frequency of all sample collections.

Instructions for the collection, handling, storage, and shipment of samples are found in the laboratory manual that will be provided. Collection, handling, storage, and shipment of samples must be under the specified, and where applicable, controlled temperature conditions as indicated in the laboratory manual.

Study-specific Materials

The investigator will be provided with the following supplies:

- IB for Ad26.RSV.preF⁸
- IB for RSV preF protein⁹
- Study Site Investigational Product and Procedures Manual
- Laboratory manual
- Investigational Product Preparation Instructions

- Participant diary and instructions for use
- Rulers (to measure diameter of any erythema and induration/swelling)
- Thermometers
- Laboratory kits
- Contact Information page(s)
- Study protocol
- IWRS Manual
- Electronic data capture (eDC) Manual/eCRF completion guidelines
- Any other manual, as applicable
- Wallet card
- Sample ICF

8.1. Immunogenicity Assessments

Venous blood samples of approximately 10 and 50 mL will be collected for the determination of humoral and cellular immune responses, respectively (Table 3), at the timepoints indicated in the Schedule of Activities (Section 1.3). Nasosorption samples using SAM strips will be collected at the timepoints indicated in the Schedule of Activities (Section 1.3), and will be used for immunogenicity assessments including, but not limited to, determination of antigen-specific immunoglobulin (IgG and IgA) (Table 3).

Sample collection and processing will be performed by the study-site personnel according to current versions of approved standard operating procedures.

Table 3: Summary of Possible Immunogenicity Assays (Humoral and Cellular)

Assay	Purpose
Primary and secondary endpoints	
Pre-F protein binding antibody (ELISA)	Analysis of antibodies binding to RSV F protein in prefusion form
RSV A2 neutralization	Analysis of neutralizing antibodies to the A2 strain
IFN- γ (ELISpot)	T-cell IFN- γ responses to RSV F protein peptides
Exploratory endpoints	
Post-F protein binding antibody (ELISA)	Analysis of antibodies binding to RSV F protein in postfusion form
Antigen-specific T-cell immune responses	Analysis of T-cell responses to RSV F protein peptide-stimulated PBMCs (including, but not limited to, CD4 $^{+}$ /CD8 $^{+}$, IL-2, IFN- γ , TNF- α , activation markers and memory) using ICS or CyTOF
RSV strain cross-neutralization	Analysis of cross-neutralizing antibodies to B and/or other A strain(s)
Antibody specificity and functional characterization	Analysis of pre- and post-F antibody specificity by functional assays such as ELISA, competition ELISA, and epitope mapping. Functional characterization of antibodies including, but not limited to, ADCC, ADCP, avidity, immunoglobulin isotype, and functional VNAs to other respiratory viruses

Analysis of nasal antibodies to RSV including, but not limited to, IgA and IgG	Analysis of nasal antibodies binding to RSV F protein in prefusion and/or postfusion form in nasal samples
Adenovirus neutralization assay	Analysis of neutralizing antibodies to Ad26
ADCC = antibody-dependent cell-mediated cytotoxicity; ADCP = antibody-dependent cellular phagocytosis; CyTOF = cytometry by time of flight; IL = interleukin; PBMC = peripheral bone marrow cell; TNF = tumor necrosis factor.	

Immunogenicity samples will be prioritized as outlined in the laboratory manual.

8.2. Safety Assessments

Safety will be evaluated throughout the study from signing of the ICF until the last study-related activity, or until the participant has been deemed lost to follow-up after demonstration of due diligence of follow-up efforts.

Key safety assessments will include the monitoring of AEs, physical examinations, vital signs, and clinical safety laboratory assessments.

AEs will be reported and followed by the investigator as specified in Section 8.3 and Section 10.3, Appendix 3.

Any clinically significant abnormalities (including those persisting at the end of the study/early withdrawal) will be followed by the investigator until clinical resolution (return to baseline) or until a clinically stable condition is reached, or until the participant has been deemed lost to follow-up after demonstration of due diligence of follow-up efforts.

Details regarding the DRC are provided in Section 9.6.

The study will include the following evaluations of safety and reactogenicity according to the timepoints provided in the Schedule of Activities (Section 1.3).

8.2.1. Physical Examinations

A physical examination (including height and body weight) will be carried out at screening (Cohorts 2 and 3) or on Day 1 (prevaccination) (Cohort 1). At all other visits, an abbreviated, symptom-directed physical examination will be performed if deemed necessary by the investigator based on clinically relevant issues, clinically relevant symptoms, and medical history. A symptom-directed physical examination may be repeated if deemed necessary by the investigator.

Physical examinations will be performed by the investigator or by a designated medically-trained clinician. Any clinically relevant abnormalities or changes in severity observed during the review of body systems should be documented in the eCRF.

8.2.2. Vital Signs

Body temperature (oral route preferred), heart rate (beats per minute), respiratory rate (breaths per minute), and systolic and diastolic blood pressure (mmHg) will be assessed.

Blood pressure and heart rate measurements will be assessed, if possible, with a completely automated device. Manual techniques will be used only if an automated device is not available.

Systolic and diastolic blood pressure (supine) and heart and respiratory rate measurements should be preceded by at least 5 minutes of rest in a quiet setting without distractions (eg, television, cell phones). Vital signs measurements should be taken before nasal sampling and blood draws, if applicable.

Confirmatory vital signs measurements can be performed if inconsistent with a prior measurement. Any clinically relevant abnormalities or changes in severity should be documented in the eCRF.

8.2.3. Clinical Safety Laboratory Assessments

In Cohorts 2 and 3, blood samples for biochemistry and hematology will be collected as noted in [Table 4](#) at the timepoints indicated in the Schedule of Activities (Section 1.3). All clinical safety laboratory analyses will be performed at the central laboratory.

Table 4: Protocol-required Clinical Laboratory Assessments

Biochemistry Panel	Hematology Panel
sodium	hemoglobin
potassium	white blood cell count with differential
creatinine	platelet count
blood urea nitrogen	prothrombin time ^a
aspartate aminotransferase	activated partial thromboplastin time ^a
alanine aminotransferase	

a. Will be measured at screening only.

Review and Grading of Laboratory Data

The investigator must review the laboratory results, document this review, and record any clinically relevant changes occurring during the study in the AE section of the eCRF. The laboratory reports must be filed with the source documents.

Laboratory values will be initially evaluated by the investigator according to central laboratory criteria. Abnormal values outside the central laboratory normal range will be graded according to the FDA Guidance document “Toxicity Grading Scale from Healthy Adult and Adolescent Volunteers Enrolled in Preventive Vaccine Clinical Trials” (Section 10.2, Appendix 2). Laboratory values within central laboratory normal limits will not be FDA graded and will be considered as normal.

Reporting Laboratory Abnormalities as AEs

Any clinically significant abnormal laboratory value within 28 days after vaccination that falls outside the central laboratory normal range will be captured as an AE. Laboratory values outside normal ranges that are not clinically significant in the judgment of the investigator should not be recorded as AEs. Any laboratory value falling within the central laboratory normal range will not be severity graded or recorded as an AE, regardless of whether the value falls within FDA ranges for Grade 1 or higher.

Repeat of Clinically Significant Laboratory Tests

For any clinically significant abnormal laboratory value that has increased in grade over baseline, the test must be repeated at the next scheduled visit or sooner based on the investigator's judgment, however Grade 3 or higher abnormalities should be retested within 48 hours.

Screening Procedures (Cohorts 2 and 3 Only)

For entry into the study, each participant must be healthy on the basis of clinical laboratory tests performed at screening. Refer to inclusion criterion 10 in Section [5.1](#) for more details.

8.3. AEs and SAEs

Timely, accurate, and complete reporting and analysis of safety information from clinical studies are crucial for the protection of participants, investigators, and the sponsor, and are mandated by regulatory agencies worldwide. The sponsor has established standard operating procedures in conformity with regulatory requirements worldwide to ensure appropriate reporting of safety information; all clinical studies conducted by the sponsor or its affiliates will be conducted in accordance with those procedures.

For further details on AEs and SAEs (Definitions and Classifications; Attribution Definitions; Severity Criteria; Special Reporting Situations; Procedures) as well as product quality complaints (PQCs), refer to Section [10.3](#), Appendix 3.

8.3.1. Time Period and Frequency for Collecting AE and SAE Information

AEs and special reporting situations, whether serious or nonserious, that are related to study procedures or that are related to noninvestigational sponsor products will be reported from the time a signed and dated ICF is obtained until the end of the study/early withdrawal.

Clinically relevant medical events not meeting the above criteria and occurring between signing of ICF and date of vaccination will be collected on the Medical History eCRF page as pre-existing conditions.

Any solicited local (injection site) or systemic AEs occurring during the 30-minute postvaccination observation period (or longer if deemed necessary by the investigator) will be documented by the study-site personnel following this observation period. Solicited AEs collected through a participant diary will be recorded from the time of vaccination until 7 days after vaccination.

All other unsolicited AEs and special reporting situations, whether serious or nonserious, will be reported from the time of vaccination until 28 days after vaccination. All AEs and SAEs leading to discontinuation of the study vaccination (regardless of the causal relationship) are to be reported from the moment of vaccination until completion of the participant's last study-related procedure, which may include contact for safety follow-up. All other SAEs (regardless of the causal relationship) are to be reported from the time of vaccination until the end of the study/early withdrawal.

All SAEs occurring during the study must be reported to the appropriate sponsor contact person by study-site personnel within 24 hours of their knowledge of the event. Information regarding SAEs will be transmitted to the sponsor using the SAE Form and Safety Report Form of the eCRF, which must be completed and reviewed by a physician from the study site, and transmitted to the sponsor within 24 hours. The initial and follow-up reports of an SAE should be transmitted electronically or by facsimile (fax).

The sponsor will evaluate any safety information that is spontaneously reported by an investigator beyond the time frame specified in the protocol.

8.3.2. Method of Detecting AEs and SAEs

Care will be taken not to introduce bias when detecting AEs or SAEs. Open-ended and nonleading verbal questioning of the participant is the preferred method to inquire about AE occurrence.

Solicited AEs

Solicited AEs are used to assess the reactogenicity of the study vaccine and are predefined local (at the injection site) and systemic events for which the participant is specifically questioned and which are noted by participants in their participant diary.

After vaccination with study vaccine on Day 1, participants will remain under observation at the study site for a minimum of 30 minutes for presence of any acute reactions and solicited events, or longer if deemed necessary by the investigator. In addition, participants will record solicited signs and symptoms in the participant diary for 7 days after vaccination. All participants will be provided with the participant diary and instructions on how to complete the diary (Section 8). The study-site personnel will transcribe the information provided by the participant into the relevant sections of the eCRF. After review and verbal discussion of the initial participant diary entries with the participant, the investigator will complete his or her own assessment in the relevant sections of the eCRF. Once a solicited sign or symptom from the participant diary is considered to be of severity Grade 1 or above during the investigator's assessment, it will be recorded as a solicited AE.

Solicited Injection Site AEs

Participants will be asked to note in the participant diary occurrences of injection site pain/tenderness at the study vaccine injection site daily for 7 days after vaccination (day of vaccination and the subsequent 7 days). The extent (largest diameter) of any erythema and swelling at the injection site should be measured (using the ruler supplied) and recorded daily. The case definitions for solicited injection site events can be found in Gidudu et al.⁷ and Kohl et al.¹¹

Solicited Systemic AEs

Participants will be instructed on how to record daily body temperature using a thermometer provided for home use. Participants should record the body temperature (oral route preferred) in the participant diary in the evening of the day of vaccination, and then daily for the next 7 days

approximately at the same time each day. If more than one measurement is made on any given day, the highest body temperature of that day will be used in the eCRF.

Fever is defined as endogenous elevation of body temperature $\geq 38.0^{\circ}\text{C}$ [$\geq 100.4^{\circ}\text{F}$], as recorded in at least one measurement.¹⁴

Participants will also be instructed on how to note signs and symptoms in the participant diary on a daily basis for 7 days after vaccination (day of vaccination and the subsequent 7 days), for the following events: fatigue, headache, nausea, and myalgia.

Unsolicited AEs

Unsolicited AEs are all AEs for which the participant is not specifically questioned in the participant diary.

8.3.3. Follow-up of AEs and SAEs

AEs, including pregnancies in partners of male participants, will be followed by the investigator as specified in Section 10.3, Appendix 3.

8.3.4. Regulatory Reporting Requirements for SAEs

The sponsor assumes responsibility for appropriate reporting of AEs to the regulatory authorities. The sponsor will also report to the investigator (and the head of the investigational institute where required) all suspected unexpected serious adverse reactions (SUSARs). The investigator (or sponsor where required) must report SUSARs to the appropriate IEC/IRB that approved the protocol unless otherwise required and documented by the IEC/IRB. A SUSAR will be reported to regulatory authorities unblinded. Participating investigators and IEC/IRB will receive a blinded SUSAR summary, unless otherwise specified.

8.3.5. Pregnancy

All initial reports of pregnancy in female participants or partners of male participants must be reported to the sponsor by the study-site personnel within 24 hours of their knowledge of the event using the appropriate pregnancy notification form. Abnormal pregnancy outcomes (eg, spontaneous abortion, fetal death, stillbirth, congenital anomalies, ectopic pregnancy) are considered SAEs and must be reported using the SAE Form.

Follow-up information regarding the outcome of the pregnancy and any postnatal sequelae in the infant will be required.

8.4. Treatment of Overdose

For this study, any dose of the Ad26/protein preF RSV vaccine greater than the protocol-specified dose will be considered an overdose. The sponsor does not recommend specific intervention for an overdose.

In the event of an overdose, the investigator or treating physician should:

- Contact the medical monitor immediately.
- Closely monitor the participant for AE/SAE and laboratory abnormalities until resolution.
- Document the quantity of the excess dose in the eCRF.
- Report as a special reporting situation.

8.5. Genetics

Genetics are not evaluated in this study.

8.6. Medical Resource Utilization and Health Economics

Health Economics/Medical Resource Utilization and Health Economics parameters are not evaluated in this study.

9. STATISTICAL CONSIDERATIONS

Statistical analysis will be done by the sponsor or under the authority of the sponsor. A general description of the statistical methods to be used to analyze the immunogenicity and safety data is outlined below. Specific details will be provided in the statistical analysis plan (SAP).

9.1. Statistical Hypotheses

No formal statistical testing of safety or immunogenicity data is planned; data will be analyzed descriptively.

9.2. Sample Size Determination

9.2.1. Immunogenicity (Cohort 1)

The primary objective of Cohort 1 is to explore the dose-response relationship of humoral immune responses (as measured by preF ELISA) induced by different dose levels of the Ad26/protein preF RSV vaccine.

Assuming:

- 10% of exclusions (eg, drop-outs, missing samples, and major protocol deviations impacting immunogenicity data)
- a standard deviation on the \log_2 scale of the preF ELISA of 1.3 on Day 15 and 1.1 on Day 183 for all dose levels
- 4 dose levels

The linear model $\log_2 (\text{preF ELISA}_{\text{timepoint}}) = \text{GMT preF ELISA}_{\text{Ad26/protein preF RSV vaccine (1x10}^{11} \text{vp/150 }\mu\text{g),timepoint}} + \text{slope} \times \# \text{titration steps}$ provides a standard error for the slope of 0.052 on Day 15 and 0.040 on Day 183 with 50 participants per arm. This is deemed sufficient for this exploratory study.

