4.3. Justification for Dose Level

The dose level of 1×10^{11} vp for Ad26.RSV.preF and 150 µg for RSV preF protein (administered in all 3 cohorts) was selected from the primary analysis of Cohort 2 in study VAC18193RSV1004 and is currently under further evaluation in studies VAC18193RSV1004 and VAC18193RSV2001 (Section 2.2.2).

The lower dose levels for Ad26.RSV.preF in Cohort 1 of the current study were selected based on the assumption that half-log intervals in dose response are biologically meaningful for vaccines.

There are currently no safety data available of Ad26.RSV.preF at a dose level above 1×10^{11} vp. Two higher dose levels of Ad26.RSV.preF (ie, 1.3×10^{11} vp [Cohort 2] and 1.6×10^{11} vp [Cohort 3]) will therefore be assessed in this study. An increase of 0.3×10^{11} vp per dose level could lead to a potential increase of target fill concentration of approximately 15%.

In all cohorts, the dose level of RSV preF protein will be kept constant (150 µg). This dose level has been tested in other (ongoing) clinical studies (Section 2.2.2).

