9.4.2. Immunogenicity Analyses

No formal statistical testing of immunogenicity data is planned. Immunogenicity data will be analyzed descriptively by cohort and group. In addition, for a selection of tables, data may be pooled over cohorts.

Descriptive statistics (eg, geometric mean and 95% confidence interval [CI] for ELISA and VNA data; median and quartiles for ELISpot) will be calculated for continuous immunologic parameters at all timepoints. For the humoral assays, geometric mean fold rises from baseline and corresponding 95% CIs might additionally be calculated. Baseline is considered as the last available assessment before vaccination. Graphical representations of immunologic parameters will be made as applicable.

Frequency tabulations will be calculated for discrete (qualitative) immunologic parameters as applicable.

To explore the dose-response relationship between preF ELISA and different dose levels of the Ad26/protein preF RSV vaccine, a linear regression model will be fitted for each timepoint separately, using data of the active groups of Cohort 1, with the log-transformed preF ELISA titers at the considered timepoint as dependent variable, the number of titration steps as independent variable, and the geometric mean titer (GMT) of preF ELISA of the Ad26/protein preF RSV vaccine (1×10^{11} vp/150 μ g) at the considered timepoint as a fixed intercept.

The linear model $\log_2(\text{preF ELISA}_{\text{timepoint}}) = \text{GMT preF ELISA}_{\text{Ad26/protein preF RSV vaccine } (1 \times 10^{11} \text{ vp/150 } \mu\text{g}), \text{timepoint}} + \text{slope} \times \# \text{titration steps}$ will initially be fitted for the active groups of Cohort 1 but may be extended in a later stage with data of the active groups of Cohorts 2 and 3. A similar model may be fitted as well for other assays.

Depending on the model fit, other models (eg, log-linear models or EMAX models) may be explored as well.

The incidence of neutralizing antibodies to Ad26 might be summarized for participants who are positive for antibodies to Ad26.

Other immunogenicity analyses may be performed to further characterize the immune responses that are generated.

The primary analysis set for the immunogenicity analysis is the PPI set. As a sensitivity analysis, key tables may also be based on the FAS.

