### 1.4. Sample Size Justification

Refer to Section 9.2 of the CTP.

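### The Day 183 slope standard error of 0.040 does not follow from the stated SD of 1.1; the formula that gives 0.052 on Day 15 gives 0.044

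*Protocol*

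**What the plan says.** Protocol Section 9.2.1 bases the Cohort 1 immunogenicity sample size on the precision of a dose-response slope. It assumes four dose levels, "10% of exclusions (eg, drop-outs, missing samples, and major protocol deviations impacting immunogenicity data", and an SD on the log2 "scale of the preF ELISA of 1.3 on Day 15 and 1.1 on Day 183 for all dose levels". It then says that the linear model "provides a standard error for the slope of 0.052 on Day 15 and 0.040 on Day 183 with 50 participants per arm", and judges this adequate for an exploratory study. The Synopsis (Section 1.1, Sample Size Determination) gives the same inputs and the same two results.

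The model is described in Protocol Section 9.4.2 and again in SAP Section 5.3.1.1. It is fitted separately at each timepoint, with "the number of titration steps as independent variable" and the geometric mean titer of the 1×10^11 vp group "at the considered timepoint as a fixed intercept". SAP Section 1.4 adds no calculation of its own: "Refer to Section 9.2 of the CTP". Neither document gives a different number of evaluable participants, exclusion rate or model for Day 183.

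**The concern.** Both standard errors come from one sentence, one model and one set of sample-size inputs; only the SD changes between the timepoints. The Day 183 value should therefore be the Day 15 value scaled by 1.1/1.3 = 0.846, or about 0.044. The stated pair has the ratio 0.040/0.052 = 0.769.

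The slope standard error is the only precision statement offered for the Cohort 1 immunogenicity objective. (The tables in Section 9.2.2 concern safety.) The 6-month preF ELISA is a named secondary endpoint under the Cohort 1 dose-response objective, and the study is meant to inform the lower release limit through immunogenicity. If 0.040 is wrong, the plan claims better Day 183 precision than its assumptions support. If 1.1 is wrong, anyone who reuses that SD for planning inherits the error.

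**Working it through.** **Inputs**

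- Randomized per active arm: 50. Exclusions: 10%. Evaluable: n = 50 × 0.9 = 45 (Section 9.2.1).
- SD of log2 titer: 1.3 on Day 15 and 1.1 on Day 183, common to all dose levels (Section 9.2.1).
- Four dose levels. Section 4.3 says the lower ones were "selected based on the assumption that half-log intervals in dose response are biologically meaningful for vaccines", so the steps are about equally spaced. I code them x = 0, 1, 2, 3, with 0 for the 1×10^11 vp group. This coding is inferred, but it fits the fixed intercept placed at that group.
- Fixed intercept, so the slope is the only coefficient estimated (Section 9.4.2; SAP Section 5.3.1.1).

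**Formula**

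With a fixed intercept, SE(slope) = SD / √(n × Σx²).

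Σx² = 0 + 1 + 4 + 9 = 14, and √(45 × 14) = √630 = 25.10.

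**Day 15, to reproduce the plan's figure**

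1.3 / 25.10 = 0.0518, which rounds to the stated 0.052. This supports the formula, the coding and the 45 evaluable per arm.

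**Day 183, same formula**

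1.1 / 25.10 = 0.0438, which rounds to 0.044. The plan states 0.040. A simulation of the fixed-intercept fit gave 0.0518 and 0.0438.

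**Could another reading give both figures?**

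| Variant | Day 15 | Day 183 |
|---|---|---|
| Stated in the plan | 0.052 | 0.040 |
| Fixed intercept, n = 45 | 0.0518 | 0.0438 |
| Fixed intercept, n = 50 (no exclusions) | 0.0491 | 0.0416 |
| Fixed intercept, n = 55 | 0.0469 | 0.0396 |
| Actual doses on a log3 scale, n = 45 | 0.0517 | 0.0437 |
| Actual doses in half-log10 units, n = 50 | 0.0514 | 0.0435 |
| Steps coded 1 to 4, n = 45 | 0.0354 | 0.0299 |
| Estimated intercept, n = 45 | 0.0867 | 0.0733 |

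None gives both. Adding the higher-dose groups of Cohorts 2 and 3, which the plan allows at a later stage, does not help. Extra participants at 1×10^11 vp sit at x = 0 and contribute nothing to Σx². Groups 7 and 10 (45 evaluable each, x about −0.24 and −0.43) raise 630 to about 641, which gives 1.1/√641 = 0.043.

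**What 0.040 would require**

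- With n = 45: SD = 0.040 × 25.10 = 1.00 (0.99 to 1.02 allowing for rounding of the standard error).
- With SD 1.1: n = (1.1/0.040)²/14 = 54 evaluable per arm. That is more than the 50 randomized, and means about 54/0.9 = 60 randomized.

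**Size**

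- Standard error: 0.0438/0.040 = 1.096, so the correct value is 9.6% above the stated one; equivalently, the stated value is 8.7% too small.
- Variance: 1 − (0.040/0.0438)² = 0.17, so it is understated by about 17%.
- SAP Section 5.3.1.1 reports a one-sided 95% lower limit for the slope. Its expected distance from the estimate at Day 183 is 1.645 × 0.0438 = 0.072 log2 units per step, against 1.645 × 0.040 = 0.066.

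**The case against.** The strongest objection is that little depends on this figure. Day 183 is a secondary timepoint, the Day 15 figure for the primary endpoint is right, no formal testing is planned, and the analysis will use the observed residual variance. The confidence limit moves by 0.006 log2 units per step. All of that stands, and it limits the weight of the point. It does not make the stated figure correct.

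A second objection is that the SDs are given to one decimal, so the ratio argument is not airtight. That is true. With SDs of 1.35 and 1.05 and 49 evaluable per arm, √(49 × 14) = 26.19, and the results are 0.0515 and 0.0401, which round to the stated pair. But this needs both SDs at opposite rounding edges, and one exclusion in 50 instead of 10%. At the plan's own 45 evaluable, an SD of 1.05 still gives 0.042. The finding therefore rests on the calculation with n = 45, not on the ratio alone.

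A third objection is that the SD may be the misprint. This also stands: SD 1.0 gives 0.0398, which rounds to 0.040. In that case the claimed precision is right and the stated assumption is wrong. The two numbers still contradict each other, and a reader cannot tell which to trust.

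**Conclusion.** The concern holds. Under the plan's own assumptions (45 evaluable per arm, steps 0 to 3, fixed intercept, SD 1.1) the Day 183 slope standard error is 0.044, not 0.040. The step coding is inferred, but it reproduces the Day 15 figure, and the other codings tried do not give both stated values. The documents do not settle whether the standard error or the SD is the wrong entry. The consequence is limited to the stated precision for a secondary timepoint. The Day 15 justification and the sample size of 50 per arm are unaffected. It should still be corrected, because it is a wrong number in the sample-size justification.

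**What to change.** Check the original calculation and correct whichever number is wrong, in both Section 9.2.1 and the Synopsis:

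- if the SD of 1.1 was intended, restate the Day 183 standard error as 0.044;
- if 0.040 was intended, restate the Day 183 SD as 1.0 and give its source.

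It would also help to state the formula, the step coding and the 45 evaluable per arm, so that the figures can be reproduced. If the sponsor separately decides to estimate the intercept, both figures change: SD/√(45 × 5) gives 0.087 on Day 15 and 0.073 on Day 183 with the stated SDs. The present correction does not depend on that choice.

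The cost is one number changed in two places. SAP Section 1.4 only refers back to the protocol and needs no edit. There is no change to design, sample size or analysis.
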